#### 1.6 Acceptability

Acceptability has been conceptualized as individuals' willingness and ability to use a product over time and, when available, in the context of a range of alternative choices. In both the fields of HIV prevention and contraception, individuals' decisions to initiate use of a product, and their ability to adhere to and sustain use of that product is strongly influenced by their knowledge and beliefs about the product, attitudes towards and experiences of product attributes and how product use fits their social/sexual context – especially in comparison to other prevention methods. As apparent from recent microbicide and PrEP clinical trials, product-related acceptability is also intertwined with the clinical trial context, including a person's understanding of the study product efficacy (which may be a placebo) and attitudes towards other trial requirements. Such factors may lead to differences between within-trial acceptability and likelihood of using a product outside of a trial context.

While assessing acceptability in a low-risk population may not be representative of the target population for PrEP, given the novelty of this investigational approach, it is believed that capturing limited and focused information on acceptability is warranted. Acceptability will be assessed through a questionnaire, including questions related to health outcomes , assessed after initiation of each injection. Semi-structured interviews may be conducted at select sites regarding their experience with study treatment. These would be conducted under a separate IRB/EC approved consent. Participation in such interviews would be optional.

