# 5.15 Procedures for Participants Who Do Not Complete the Full Course of Injections

Participants who received the Week 5 (Injection #1) and Week 17 (Injection #2) injections but will not receive the final injection (Injection #3) will be followed for 52 weeks after their Week 17 injection, through to Week 69. Because participants meeting these criteria received an injection at Week 5 and Week 17, the procedures for Weeks 6, 9, 13, 18, and 23 Safety Visits as outlined above and in the Schedule of Evaluations and Procedures will remain the same. Procedures for subsequent study visits for these participants are outlined in Appendix II.

Participants who received the Week 5 injection (Injection #1) and will not receive the next two injections will be followed for 52 weeks after their Week 5 injection, through to Week 57. Because participants meeting these criteria received an injection at Week 5, the procedures for Weeks 6, 9, and 13 Safety Visits as outlined above and in all Schedule of Evaluations and Procedures will remain the same. Procedures for subsequent visits for these participants are outlined in Appendix III.

Participants who are unable to receive the first injection for any reason will be terminated from the study. If the reason is due to HIV infection or pregnancy, refer to Section 5.17 and 5.19, respectively.

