# 7.1.2 Secondary Endpoints

- Proportion of participants who discontinue either oral or injectable study product for reasons
  of toxicity, tolerability, or acceptability prior to completion of the full oral and injectable
  phases
- Proportion of participants experiencing Grade 2 or higher clinical AEs and laboratory abnormalities during 52 weeks following final injection (safety) and any AE that leads to discontinuation (tolerability) during the aggregate oral and injectable phases
- Proportion of participants experiencing Grade 2 or higher clinical AEs and laboratory abnormalities (safety) and any AE that leads to discontinuation (tolerability) in the oral phase and washout period
- Plasma drug levels of GSK1265744 at designated time points after each injection of 744LA
- Plasma drug levels of GSK1265744 at designated time points after each injection of 744LA stratified by age, gender, race, ethnicity, weight, BMI, and smoking status
- Proportion of participants willing to use an injectable agent such as the study product for HIV prevention in the future
- Change from enrollment of self-reported sexual behavior (number of sexual partners, episodes of unprotected anal and/or vaginal intercourse) during the study period using a standardized assessment tool
- Number of incident HIV infections through the study period, including number with treatment emergent resistance
- Proportion of injectable hormonal-contraception-using female participants who reach a safety or tolerability endpoint as defined above

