The tolerability of 744LA will be measured by the proportion (with 95% CI) of participants who terminate from receiving injections prior to the full course due to AE, intolerability of injection, frequency of injections, or burden of procedures related to injections out of those subjects that received at least one injection by treatment arm. Table 4 shows two-sided 95% confidence intervals for true tolerability rate based on various possible observed rates, given the sample size of 120 participants in the 744LA arm.

The acceptability of 744LA will be measured by the proportion (with 95% CI for the 744 LA arm) of participants who would consider using 744LA for HIV prevention in the future. This endpoint will be measured at the end of the study on every enrolled participant (including those who terminated product use during the trial). Table 6 shows two-sided 95% confidence intervals for true acceptance rate based on various possible observed rates, given the sample size of 120 participants in the active 744LA arm

Table 6: 95% Confidence Intervals for the True Acceptance Rate Given Possibly Observed Rates

N	Observed Event Rate	95% CI for True Event Rate
	50%	(41.2%, 58.8%)
	70%	(61.3%, 77.5%)
Arm 1: 120 (744LA)	80%	(72%, 86.2%)
	90%	(83.3%, 94.2%)
	95%	(89.5%, 97.7%)

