# 7.6.3 Secondary Analyses

### Acceptability

To assess acceptability of the 744LA, the proportion (with 95% CI for the 744LA arm) of subjects who would consider using 744LA for HIV prevention in the future will be calculated among all enrolled participants (including those who terminated product use during the trial) and summarized by treatment arm.

A questionnaire modeled after the HIV Treatment Satisfaction Questionnaire (HIVTSQ) will also be used to assess participant acceptability and satisfaction to the treatment. For each question the responses will be summarized by the proportion of participants reporting the response on the Likert scale out of all those that answered the question by visit and treatment arm. An overall treatment satisfaction score will be calculated for each participant by visit. These total scores will be summarized by visit and treatment arm.

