**APPENDICES I-VII** 

Appendix I: Schedule of Procedures and Evaluations – For Participants Who Complete All Three Injections

Appendix I: Schedule of Procedures and Evaluations – For Pa					arue										
		Oral Phase					Injection And Tail Phase Follow-up								
	Screening	Day 0 Enr	Week 2 Safety	Week 4 Post Oral Drug	1-WEEK WASHOUT	Week 5 First Injection	Week 6, 9, 13 Safety	Week 17 Second Injection	Week 18, 23 Safety	Week 29 Third Injection	Week 30, 35 Safety	Week 41 Primary Endpoint	Week 53, 65, 77 Tail Phase	Week 81 Final Visit	
ADMINISTRATIVE, BEHAVIORAL	, REGULATO	RY													
Informed consent	X														
Locator information	X	X	X	X		X	X	X	X	X	X	X	X		
Demographic information		X													
Randomization		X													
HIV counseling	X	X	X	X		X	X	X	X	X	X	X	X	X	
Offer condoms and lubricant	X	X	X	X		X	X	X	X	X	X	X	X	X	
Acceptability assessment (Weeks 6, 18, 30 only)							X		X		X				
Behavioral assessment		X				X		X		X		X	X		
Adherence counseling/pill count 		X	X	X											
CLINICAL EVALUATIONS & PROC	CEDURES														
History (including bleeding history at Screening), con meds, physical exam 	X	X	X	X		X	X	X	X	X	X	X	X	X	
ECG 	X	X		X			X		X		X				
Blood collection	X	X	X	X		X	X	X	X	X	X	X	X	X	
Urine collection for GC/CT testing men and women 	X									X			X		
Urine collection for urinalysis		X										X			
Urine pregnancy testing 	X	X	X	X		X		X		X		X	X	X	
Rectal swab for GC/CTtesting men and women 		X								X			X		
Vaginal swab for GC/CT testing  (Optional alternate collection for women if urine not used)	X									X			X		
Provide oral study drug		X													
Administer injection 						X		X		X					
ISR evaluation							X		X		X				
LOCAL LABORATORY EVALUATI	1	CEDURI	1	1					ı	1	ı	1			
HIV testing 	X	X	X	X		X	X	X	X	X	X	X	X	X	
HBV and HCV testing 	X														
CBC with differential	X	X	X	X		X	X	X	X	X	X	X			
Chemistry testing 	X	X	X	X		X	X	X	X	X	X	X			
LFTs (AST, ALT, total bilirubin, alkaline phosphatase)	X	X	X	X		X	X	X	X	X	X	X	X	X	

		Oı				Injection And Tail Phase Follow-up									
	Screening	Day 0 Enr	Week 2 Safety	Week 4 Post Oral Drug	1-WEEK WASHOUT	Week 5 First Injection	Week 6, 9, 13 Safety	Week 17 Second Injection	Week 18, 23 Safety	Week 29 Third Injection	Week 30, 35 Safety	Week 41 Primary Endpoint	Week 53, 65, 77 Tail Phase	Week 81 Final Visit	

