Appendix II: Schedule of Procedures and Evaluations – For Participants Who Complete Two Injections Only

Appendix II: Schedule		idi es dire	Livuluulo			se Follow-up	inpiece 1	Wo Hijeedic	ins only
	Week 5 First Injection	Week 6, 9, 13 Safety	Week 17 Second Injection	Week 18, 23 Safety	Week 29 Follow Up	Week 41 Follow Up	Week 53 Follow Up	Week 65 Follow Up	Week 69 Final
ADMINISTRATIVE, BEHAV	VIORAL, RE	GULATOI	RY						
Locator information	X	X	X	X	X	X	X	X	
HIV counseling	X	X	X	X	X	X	X	X	X
Offer condoms and lubricant	X	X	X	X	X	X	X	X	X
Acceptability assessment (Week 6 and 18 only)		X		X					
Behavioral assessment	X		X		X	X	X	X	
CLINICAL EVALUATIONS	& PROCED	URES							
History, con meds, physical exam 	X	X	X	X	X	X	X	X	X
ECG 		X		X					
Blood collection	X	X	X	X	X	X	X	X	X
Urine collection for GC/CT testing men and women 					X		X		
Urine pregnancy testing 	X		X		X	X	X	X	X
Rectal swab for GC/CT testing men and women 					X		X		
Vaginal swab for GC/CT testing  (Optional alternate collection for women if urine not used)					X		X		
Administer injection 	X		X						
ISR evaluation		X		X					
LOCAL LABORATORY EVALUATIONS									
HIV testing 	X	X	X	X	X	X	X	X	X
CBC with differential	X	X	X	X	X				
Chemistry testing 	X	X	X	X	X				

		Injection And Tail Phase Follow-up							
	Week 5 First Injection	Week 6, 9, 13 Safety	Week 17 Second Injection	Week 18, 23 Safety	Week 29 Follow Up	Week 41 Follow Up	Week 53 Follow Up	Week 65 Follow Up	Week 69 Final
LFTs (AST, ALT, total bilirubin, alkaline phosphatase)	X	X	X	X	X	X	X	X	X
Syphilis serologic testing men and women 					X		X		
Urine/vaginal swab GC/CT testing men and women 					X		X		
Plasma storage 	X	X	X	X	X	X	X	X	X
Plasma storage for Pharmacology testing 	X	X	X	X	X	X	X	X	X

SEE FOOTNOTES FOR APPENDIX I

Appendix III: Schedule of Procedures and Evaluations – For Participants Who Complete One Injection Only

Appendix III: Schedule of Pro	cedures und	L valuation		And Tail Phase		e one inject	Jon Omy
	Week 5 First Injection	Week 6, 9, 13 Safety	Week 17 Follow Up	Week 29 Follow Up	Week 41 Follow Up	Week 53 Follow Up	Week 57 Final Visit
ADMINISTRATIVE, BEHAVIORAL	, REGULATO	RY				 	
Locator information	X	X	X	X	X	X	X
HIV counseling	X	X	X	X	X	X	X
Offer condoms and lubricant	X	X	X	X	X	X	X
Tolerability/Acceptability Assessment (Week 6 only)		X					

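### The acceptability endpoint is defined at the end of the study in everyone enrolled, but it is scheduled only one week after each injection, so it cannot be produced as defined

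*Protocol*

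**What the plan says.** Protocol Section 7.1.2 lists the secondary endpoint without a time point: "Proportion of participants willing to use an injectable agent such as the study product for HIV prevention in the future". Section 7.2 fixes both time and population: "This endpoint will be measured at the end of the study on every enrolled participant (including those who terminated product use during the trial". Section 7.6.3 keeps the population, saying that the proportion "will be calculated among all enrolled participants", again with those who stopped product included.

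The schedules say something else:

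- Appendix I (three injections): "Acceptability assessment (Weeks 6, 18, 30 only". Final visit Week 81.
- Appendix II (two injections): "Acceptability assessment (Week 6 and 18 only". Final visit Week 69.
- Appendix III (one injection): "Tolerability/Acceptability Assessment (Week 6 only". Final visit Week 57.

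The visit lists in Sections 5.5, 5.7 and 5.9 agree with the appendices. Section 1.6 also describes the questionnaire as "assessed after initiation of each injection". On people who never reach an injection, Section 5.15 says: "Participants who are unable to receive the first injection for any reason will be terminated from the study". It sends HIV infection and pregnancy to Sections 5.17 and 5.19.

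**The concern.** The stated time point and population do not match the data that will be collected. Nobody has an acceptability assessment scheduled at the end of the study, and some of those in the denominator have none scheduled at all.

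The gap falls on the group that Section 7.2 takes care to include, those who stopped product. A participant who stops after one injection is asked once, at Week 6, and not again on that schedule through Week 57. A participant who leaves in the oral phase has no scheduled assessment.

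Acceptability is part of the stated study purpose and a named secondary objective. The protocol itself sets the definition and the schedule, and they disagree. An analysis plan can choose among collected responses but cannot supply responses that no visit asked for.

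**Working it through.** **1. Definition against schedule.** The gap is the final visit minus the last scheduled assessment.

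| Injections received | Assessments | Final visit | Gap |
|---|---|---|---|
| Three (Appendix I) | Weeks 6, 18, 30 | Week 81 | 81 − 30 = 51 weeks |
| Two (Appendix II) | Weeks 6, 18 | Week 69 | 69 − 18 = 51 weeks |
| One (Appendix III) | Week 6 | Week 57 | 57 − 6 = 51 weeks |
| None | none scheduled | terminated (Section 5.15), or limited follow-up for HIV or pregnancy (Sections 5.17, 5.19) | not applicable |

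Sections 5.2 and 5.3 (oral phase), 5.10 (Week 41), 5.11 (tail visits) and 5.12 (Week 81) list no acceptability item. The behavioral assessment does run through the tail, but Section 1.7 describes it as sexual risk behavior, and it is absent from the final visits at Weeks 81, 69 and 57.

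**2. The plan's own figure.** Table 6 uses n = 120 in the 744LA arm. I used the Wilson score interval, the method cited for Table 4, with p = 0.80 and z = 1.96:

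- Centre: (p + z²/2n)/(1 + z²/n) = (0.80 + 0.0160)/1.0320 = 0.791
- Half-width: z·√[p(1 − p)/n + z²/4n²]/(1 + z²/n) = 1.96 × 0.0374/1.0320 = 0.071
- Interval: 72.0% to 86.2%, as printed

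The other four rows of Table 6 also reproduce, so its arithmetic is sound. Its n is the number expected at Week 41 (Section 7.2).

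**3. Precision is not the issue.** At 80% observed, the interval is 72.4% to 85.9% with all 132 enrolled in the active arm. It is 71.7% to 86.4% with about 112, the number expected at Week 81 at 90% annual retention (132 × 0.9^(81/52) = 112.0).

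**4. How many may never be assessed.** At 90% annual retention, the active arm at Week 6 is expected to hold 132 × 0.9^(6/52) = 130.4, so about 2 are lost before the first assessment. The documents give no rate for oral-phase discontinuation, and terminations before the first injection could raise this number. I therefore take 2 to 5 as an assumed range.

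**5. Effect on the proportion.** Let k of 132 have no assessment and 80% of the rest be willing. The all-enrolled proportion lies between 0.80(132 − k)/132, with all k unwilling, and [0.80(132 − k) + k]/132, with all k willing.

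| k | All k unwilling | All k willing |
|---|---|---|
| 2 | 104/132 = 78.8% | 106/132 = 80.3% |
| 5 | 101.6/132 = 77.0% | 106.6/132 = 80.8% |

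The lower bound falls by 0.80/132, about 0.6 percentage points, for each never-assessed participant counted unwilling. This covers missing responses only. It does not measure changes of mind during the 51 weeks after the last assessment, for which the documents give no figure.

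**The case against.** The strongest counter-argument is that the schedule is coherent and only one phrase in Section 7.2 is out of line. The objective concerns the acceptability of the injections, Section 1.6 plans assessment after each injection, the schedules deliver that, and Sections 7.1.2 and 7.6.3 give no time point. A willingness proportion can be calculated among injected participants from their last post-injection answer. This stands as far as it goes, and it is why rewording is an acceptable second fix. It does not remove the all-enrolled population, which Section 7.6.3 repeats.

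A second argument is that early leavers may be asked anyway. Section 3.6 calls for every reasonable effort at a final evaluation, with procedures guided by the Clinical Management Committee. Sections 5.17 and 5.19 leave some oral-phase follow-up to the SSP Manual, which is not shown. So I say only that no assessment is scheduled, not that none will happen. Nothing in the protocol puts the question in those evaluations.

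Three stronger readings are tempting and do not hold:

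- **Willingness is biased upward.** A reader might infer this because those who stop are asked early or not at all. Overstatement is plausible but not shown. Someone who rejects the product after the first injection may already say so at Week 6. Stopping can also follow from HIV infection, pregnancy or laboratory toxicity rather than dislike. And asking one week after an injection is close to the reaction period (Section 1.4 gives median durations of about 5 days for pain and 22 for nodules), which could lower stated willingness.
- **An observed 80% could really be 72.7%.** That figure, 0.80 × 120/132 = 96/132, needs 12 never-assessed, unwilling participants. Twelve is the planned shortfall at Week 41 (132 − 120), not the number without a Week 6 answer, and the documents do not support it.
- **The arms are necessarily measured at different times.** Placebo follow-up may end at unblinding, but Section 5.16 expects some placebo participants to complete the full schedule. The confidence interval is planned for the 744LA arm only.

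**Conclusion.** The inconsistency is real: with the visits as scheduled, the endpoint in Section 7.2 cannot be produced. Both the time point and the denominator are unobtainable, and the responses cannot be recovered after the fact.

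The numerical effect of missing responses is probably modest: 80% becomes 78.8% to 77.0% in the active arm. This rests on 2 to 5 of 132 never being assessed (an assumption, with about 2 following from 90% annual retention), 80% willing among the rest, and every missing answer counted unwilling. The direction of any bias is unknown.

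The endpoint is secondary and descriptive, has no decision rule, and affects neither the primary endpoints nor participant safety. Section 1.6 asks only for limited information on acceptability. It should be fixed, but a reader who inferred that the trial cannot proceed without the change would be going too far.

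**What to change.** **Preferred.** Add the future-use item to the Week 41 visit in Appendices I, II and III, and to the visit at which product is permanently stopped or participation ends early, including in the oral phase. Week 41 exists on all three schedules, is common to both arms and precedes the planned unblinding. In Section 7.2, replace the end-of-study wording with this rule: the Week 41 response, or the stopping or termination response where there is no Week 41 visit. Bring Section 7.6.3 into line. The cost is one questionnaire item at existing visits plus text edits. It must be settled before participants pass those visits.

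**Alternative.** Leave the schedules alone and restate Sections 7.2 and 7.6.3 as the last post-injection response among participants who received at least one injection. This needs no new data. The cost is a narrower stated population, with no information from people who left in the oral phase.

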# 7.3 Accrual, Follow-up, and Retention

A total of 176 participants will be enrolled in approximately 16 to 24 weeks. Study participants will receive oral tablets for 4 weeks, followed by a 1 week wash out period, followed by receipt of injections at 3 time points over 24 weeks. Participants in the active drug arm will be followed for 52 weeks (12 months) after their last injection. Participants in the placebo arm will be followed until 52 weeks after their last injection or until the last participant in the active study product arm completes their Week 41 visit, whichever comes first, at which time the study will be unblinded to assess the primary endpoint. From that point on, placebo participants will no longer be followed.

The protocol team will be targeting an average annual retention rate of 90 percent.

# 7.4 Random Assignment

Enrolled participants will be assigned 3:1 at random to one of two study arms stratified by gender. The randomization scheme will be generated, operationalized and maintained by the HPTN SDMC. Additional details regarding the process of randomization will be included in the SSP Manual.

### 7.5 Blinding

Study site staff, with the exception of the site Pharmacist of Record or their designee, and participants will be blinded to the random assignments. Blinding will be maintained until the last participant enrolled in to the active drug arm has completed their Week 41 visit (the time point of the primary endpoint of the study), and when all data related to the Week 41 visit has been entered into the database, as well as cleaned and verified. At a specified time directed by the HPTN SDMC, participants will be unblinded to their treatment assignment, and participants in the placebo arm will no longer need to be followed. Participants in the active study product arm will continued to be followed for 52 weeks after their last injection. In addition, as noted in Section 5.16, an Investigator can request unblinding to the CMC in the event that a participant becomes infected with HIV during the study, and the CMC will assist in the treatment of the participant's HIV infection.

NOTE: Samples may be unblinded in the HPTN Pharmacology Laboratory (only), so the relevant assays are only performed on participants who received the study product.

# 7.6 Data and Safety Monitoring Analysis

# 7.6.1 Study Monitoring Committee

Data and Safety Monitoring Board oversight is not planned for this study. The HPTN SMC will conduct interim reviews of study progress, including rates of participant accrual, visit retention, completion of primary and main secondary endpoint collection, and, in a closed report, safety data by arm. The frequency and content of SMC reviews will be determined prior to the start of the study and outlined in the SSP Manual.

# 7.6.2 Primary Analyses

All participants who receive at least one injection will contribute to the primary analyses.

When the use of descriptive statistics to assess group characteristics or differences is required, the following methods will be used: for categorical variables, the number and percent in each category; for continuous variables, the mean, median, standard deviation, quartiles and range (minimum, maximum). Within-treatment group assessment of the change from the baseline measurement to a follow-up measurement will be analyzed using McNemar test (for categorical response variables) or the paired t-test or Wilcoxon signed-ranks test (for continuous variables). When use of formal testing to assess differences between users of the placebo arm and users of 744LA is required, the following methods will be used: for binomial response variables, chisquare tests and logistic regression (or exact testing methods); for continuous variables, t-tests and linear regression or nonparametric methods if data are non-normal.

To assess the adequacy of the randomization, participants in each of the two arms will be compared for baseline characteristics including demographics and laboratory measurements using descriptive statistics only.

